# Table 6.2.Baseline and Postbaseline Definitions and Patient Population by
Study Period and Type of Analysis

Study Period/Analysis	Patient Population	Baseline Observations	Postbaseline Observations
Lead-In Period			

TEAEs	All Enrolled Patients	Prior to first dose of open-label insulin lispro (or Visit 2 date if the dose date is missing)	The entire lead-in period after first dose of open-label insulin lispro and prior to the first dose of IP (or Visit 8 date if the dose date is missing)
Basal, prandial, and total insulin doses, and prandial/total insulin dose ratio	All Randomized Patients	Visit 2	Visits 3–8 prior to initiation of IP
Weight MMRM and ANCOVA	All Randomized Patients	Last of Visits 1-2	Visits 3–8 AND Last of Visits 3-8
26-Week Treatment P	Period (including Safety	Follow-Up Visit wher	e applicable)
HbA1c MMRM and ANCOVA	All Randomized Patients with a baseline and at least 1 postbaseline observation while on IP	Last of Visits 7-8	Visits 11, 13, 15, and 18 prior to discontinuation of IP AND Last of Visits 9-18 prior to discontinuation of IP

Study	Patient Population	Baseline	Postbaseline Observations
Period/Analysis		Observations	
HbA1c categorical analyses longitudinal logistic regression and LOCF logistic regression	All Randomized Patients with a baseline and at least 1 postbaseline observation while on IP	Last of Visits 7-8	Visits 11, 13, 15, and 18 prior to discontinuation of IP AND Last of Visits 9-18 prior to discontinuation of IP
1-hr and 2-hr PPG and other MMTT variables	All Randomized Patients with a postbaseline observation while on IP	Visit 8 prior to initiation of IP	Visit 18 prior to discontinuation of IP
10-point SMBG, basal, prandial, and total insulin doses, prandial/total insulin dose ratio	All Randomized Patients with a baseline and at least one postbaseline observation	Visit 8 prior to initiation of IP	Visits 15, and 18 prior to discontinuation of IP AND Last of Visits 9 to 18 prior to discontinuation of IP
1,5-AG	All Randomized Patients with a baseline and at least 1 postbaseline observation	Visit 8 prior to initiation of IP	Visits 11, 15, and 18 prior to discontinuation of IP AND Last of Visits 9-18 prior to discontinuation of IP
Health outcomes: ITSQ, EQ-5D-5L, EQ-VAS, WPAI-GH	All Randomized Patients with a baseline and a postbaseline observation	Last of Visits 1-8	Last of Visits 9-18 prior to discontinuation of IP

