A listing of anti-insulin lispro antibody at each visit will be provided. The listing will include antiinsulin lispro antibody status (detected/not detected), anti-insulin lispro antibody percent binding, TEADA status (positive/negative), insulin cross-reactivity status, insulin cross-reactivity percent binding for the safety population.

Subgroup analysis for the following selected efficacy and safety variables will be performed by the TEADA status during the treatment period of Visit2 to Visit 801:

- Use data prior to discontinuation of IP:
  - HbA1c and change from baseline in HbA1c
  - 1-hour and 2-hour PPG excursions
  - o basal, prandial, and total insulin dose
  - event rate (per patient per year) of overall hypoglycemic events
- Use all data regardless of IP use:
  - o treatment-emergent injection site reaction and hypersensitivity reaction

The analyses for HbA1c and change from baseline in HbA1c will be performed using an MMRM model for the primary analysis and the HbA1c data prior to discontinuation of IP. The model will include additional fixed terms of subgroup, subgroup by treatment interaction, subgroup by visit interaction, and 3-way interaction of treatment, subgroup, and visit.

The PPG excursions will be analyzed by the ANCOVA model same as the model specified in Section 6.11.2. with data collected before permanent discontinuation of IP. The model will include additional terms of subgroup, subgroup by treatment interaction, subgroup by visit interaction, and 3-way interaction of treatment, subgroup, and visit.

The subgroup analysis for insulin dose will use the MMRM model specified in Section 6.11.5 using data collected before permanent discontinuation of IP. The model will include additional fixed terms of subgroup, subgroup by treatment interaction, subgroup by visit interaction, and 3-way interaction of treatment, subgroup and visit.

The treatment emergent injection site reaction and hypersensitivity reaction will be analyzed by a logistic regression model including terms of treatment, subgroup, and treatment by subgroup interaction. All data regardless of IP use will be used for this analysis.

The negative binomial regression model specified in Table 6.5 with additional terms of subgroup, treatment by subgroup interaction will be used for the subgroup analysis of overall hypoglycemia event rate while on IP.

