The interaction effects (3-way for MMRM and 2-way for ANCOVA/logistic regression model/negative binomial regression model) will be evaluated using a significance level of 0.10, unadjusted. If the interaction effect is significant (p<0.10), separate analyses without the terms related to the subgroup will be performed for each subpopulation.

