#### 6.13. Subgroup Analyses

#### 6.13.1. Subgroup Analyses for HbA1c

The following subgroups will be analyzed for HbA1c if there are sufficient numbers of patients per group (for example, at least 10% in each group) using data collected from all randomized patients prior to discontinuation of IP through Week 26:

- age (<40,  $\geq40$  years)
- hemoglobin A1c stratum ( $\leq 8.5\%$  vs. > 8.5%)
- sex (male vs. female)
- body mass index (<25 vs.  $\geq$ 25, and <30 vs.  $\geq$ 30 kg/m^2)
- duration of diabetes (using the median as the cut-off)
- race
- country
- baseline 1-hour PPG excursion (≤ baseline median, > baseline median)
- baseline 1-hour PPG (PPG  $\leq 180 \text{ mg/dl}, >180 \text{ mg/dl})$

- baseline 2-hour PPG excursion (≤ baseline median, > baseline median)
- baseline 2-hour PPG (PPG  $\leq 180 \text{ mg/dl}, >180 \text{ mg/dl})$
- type of basal insulin during the lead-in period (glargine U-100 vs. degludec U-100)
- prandial insulin dosing plan (carbohydrate counting or pattern adjustment)

Analyses for HbA1c and change from baseline in HbA1c will be performed using an MMRM model that includes the same fixed effects given for the primary analysis model plus factors of subgroup, 2-way interaction of subgroup and treatment, 2-way interaction of subgroup and visit, and 3-way interaction of treatment, visit and subgroup. The interaction of subgroup and treatment at the primary endpoint will be evaluated to assess the treatment by subgroup interaction. When analyzing HbA1c stratum as a subgroup the baseline HbA1c will not be included as a covariate to avoid confounding. The subgroup interaction effect will be evaluated using a significance level of 0.10, unadjusted.

Additional subgroup analyses may also be performed.

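### For HbA1c and insulin dose, the antibody (TEADA) subgroup analysis tests whether the treatment-by-TEADA difference changes between visits, not whether it exists at Week 26

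*SAP*

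**What the plan says.** SAP 6.12.7.1 plans subgroup analyses by TEADA status. HbA1c, change in HbA1c, and basal, prandial and total insulin dose are analysed by MMRM with these added terms: "subgroup, subgroup by treatment interaction, subgroup by visit interaction, and 3-way interaction of treatment, subgroup, and visit". PPG excursions use ANCOVA, injection site and hypersensitivity reactions use logistic regression, and the overall hypoglycemia rate uses negative binomial regression.

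The section then states which interaction is judged: "The interaction effects (3-way for MMRM and 2-way for ANCOVA/logistic regression model/negative binomial regression model) will be evaluated". The test "will be evaluated using a significance level of 0.10, unadjusted", and it has a consequence: "If the interaction effect is significant (p<0.10), separate analyses without the terms related to the subgroup will be performed for each subpopulation".

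SAP 6.13.1 adds the same terms to the same HbA1c model for the other subgroups but names a different test: "The interaction of subgroup and treatment at the primary endpoint will be evaluated to assess the treatment by subgroup interaction".

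Table 6.2 gives the visits in each model. For HbA1c they are "Visits 11, 13, 15, and 18 prior to discontinuation of IP" (Weeks 4, 8, 12 and 26 in the protocol's Schedule of Activities). For insulin dose they are "Visits 15, and 18 prior to discontinuation of IP" (Weeks 12 and 26).

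**The concern.** The purpose of a TEADA subgroup analysis is to see whether the treatment effect differs by antibody status. In a model that already holds treatment-by-TEADA, the treatment-by-TEADA-by-visit term answers another question: does that difference move from one visit to the next? A difference that is present throughout at the same size leaves nothing in the 3-way term.

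The 0.10 rule rests on this test, so it can err both ways. A steady difference would usually go unflagged, and the nonsignificant result could be read as reassurance. A difference seen only at the early visits could trigger the separate analyses although none remains at Week 26.

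A near-constant difference is plausible. TEADA status is one classification per patient for the whole period. Dose is modelled only at Weeks 12 and 26, the ends of a maintenance phase in which protocol 5.4 expects little change in insulin dose. A dose difference established by Week 12 and then held would be close to invisible to the 3-way term.

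**Working it through.** **Plan's own figure, as a check on the inputs.** SAP 5.2: 149 completers per arm, SD 1.1, margin 0.4, true difference 0, two-sided 95% CI.
- SE = 1.1 × √(2/149) = 0.1274.
- Power = Φ(0.4/0.1274 − 1.96) = Φ(1.18) = 88.1%; with noncentral t on 296 df, 87.9%. The SAP states 87%, so the inputs reproduce to within about one point.
- The documents give no power figure for the TEADA test.

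**What the 3-way term tests.** Let d(v) be the treatment-by-TEADA difference at visit v.
- HbA1c, 4 visits: the 3-way hypothesis is d(4) = d(8) = d(12) = d(26), with 3 df.
- Dose, 2 visits: it is d(12) = d(26), with 1 df.
- The Week 26 contrast tests d(26) = 0, with 1 df.

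If d is constant, every visit-to-visit difference is zero. The noncentrality is then exactly 0 and the rejection rate is 10%, whatever the effect size, TEADA share or correlation.

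**Inputs for HbA1c power.** From the SAP: 149 per arm, SD 1.1 (taken as the same at every visit), alpha 0.10. Assumed, not in the documents: TEADA-positive share q = 0.30, equal in both arms; correlation ρ = 0.6 between all pairs of visits; the interaction profiles below. Complete data; no gain from covariates.

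**Formulas.**
- V = SD² × [2/(149q) + 2/(149(1−q))] = 1.21 × (2/44.7 + 2/104.3) = 0.0773; SE = 0.278.
- Week 26 contrast, for d(26) = 0.5: 0.5/0.278 = 1.80; power = Φ(1.80 − 1.645) = 56%.
- 3-way test: noncentrality λ = Σ(d(v) − mean d)² / [V(1−ρ)], with V(1−ρ) = 0.0309; power from the noncentral chi-square on 3 df.

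| Interaction at Weeks 4, 8, 12, 26 | Σ(d − mean)² | λ | 3-way test | Week 26 contrast |
|---|---|---|---|---|
| Constant 0.5, 0.5, 0.5, 0.5 | 0 | 0 | 10% | 56% |
| Early-building 0.2, 0.4, 0.5, 0.5 | 0.06 | 1.94 | 29% | 56% |
| Late-building 0, 0.1, 0.3, 0.5 | 0.1475 | 4.77 | 55% | 56% |
| Transient 0.4, 0.2, 0, 0 | 0.11 | 3.56 | 44% | 10% |

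**Range over the assumed TEADA share** (298 completers, SD 1.1, ρ = 0.6).
- q = 0.10: V = 1.21 × (2/14.9 + 2/134.1) = 0.180, SE 0.425. Constant 0.5: Week 26 contrast 32%, 3-way 10%. Transient: λ = 0.11/(0.4 × 0.180) = 1.52, 3-way 25%.
- q = 0.50: V = 1.21 × (2/74.5 + 2/74.5) = 0.0650, SE 0.255. Constant 0.5: Week 26 contrast 62%, 3-way 10%. Transient: λ = 0.11/(0.4 × 0.0650) = 4.23, 3-way 50%.

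**Simulation check.** 4000 runs, unstructured covariance, 298 completers, 30% positive, correlation 0.7. For constant interactions of 0.6, 0.8 and 2.0 points the 3-way test rejected in 10.4%, 10.2% and 9.5% of runs. The Week 26 contrast rejected in 69%, 90% and 100%.

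**The case against.** **The wording may be loose.** The Week 26 contrast is built from the 3-way cell means, so naming the 3-way term could be shorthand for that contrast. This does not hold up. The sentence sets 3-way against 2-way, which is the language of model terms, and SAP 6.11.1 bases significance tests on LS means and Type III tests. SAP 6.13.1 shows that the authors say so when they mean the contrast at the primary endpoint. At the least, the two sections are unreconciled.

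**Little is withheld.** The 0.10 rule controls only the separate refits. The combined model is fitted regardless, and SAP 6.1 promises LS means and treatment differences with 95% CIs from the analysis models. This stands in part: display by TEADA status is not spelled out, but nothing rules it out. A reader might infer that the separate analyses would never be produced; under a constant interaction they would still appear about 10% of the time.

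**The loss depends on the profile.** This stands. For the late-building profile the two tests are nearly equal, and the constant case is the extreme. At 10% TEADA-positive the Week 26 contrast itself has only 32% power.

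**Scope.** A reader might take all the antibody subgroup analyses to be affected. The documents do not support that: PPG excursions, injection site and hypersensitivity reactions, and hypoglycemia rate are judged by the 2-way term. The PPG paragraph does add visit terms ("The model will include additional terms of subgroup, subgroup by treatment interaction, subgroup by visit interaction", and the 3-way term) to an ANCOVA with one post-baseline visit. Those terms are redundant there, and the 2-way term is still the one tested, so this is an editorial carry-over. Only the constrained longitudinal fallback in SAP 6.11.2 would have a visit factor.

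**Importance.** Immunogenicity is a tertiary/exploratory objective with TEADA incidence as its endpoint, and it lies outside the multiplicity scheme. TEADA status is determined after randomization, with data up to Visit 801, so no interaction test on it gives a clean causal answer. All of this stands and limits the weight of the point.

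**Conclusion.** The point holds for the MMRM outcomes only: HbA1c, change in HbA1c, and basal, prandial and total insulin dose. For these, the test in SAP 6.12.7.1 has no power beyond its 10% alpha against a treatment-by-TEADA difference that is constant over visits. That result is exact and needs no assumption about effect size, TEADA share or correlation.

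The size of what is lost does rest on assumptions. With 298 completers, SD 1.1, 30% TEADA-positive and correlation 0.6, it is 10% against 56% for a constant 0.5-point HbA1c interaction. Over shares of 10% to 50%, the Week 26 contrast has 32% to 62%. The transient profile triggers the 3-way test 44% of the time (25% to 50% over those shares), against 10% for the contrast.

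A reader might go further and conclude that efficacy inference is compromised. It is not: the primary and multiplicity-adjusted conclusions do not depend on this analysis. The point is worth correcting because SAP 6.13.1 already has the suitable test for the same endpoint and the correction is nearly free.

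**What to change.** In SAP 6.12.7.1, replace the 3-way term as the effect judged for MMRM outcomes with the treatment-by-TEADA contrast at Week 26 (Visit 18) from the same MMRM, in line with SAP 6.13.1. Apply the 0.10 rule for separate analyses to that contrast, for both HbA1c and dose. Keep the 3-way term in the model.

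It would also help to state that treatment differences with 95% CIs are reported for each TEADA group whatever the p-value, so that a nonsignificant test is not taken as evidence of no difference.

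As an editorial clean-up with no inferential effect, drop the subgroup-by-visit and 3-way terms from the PPG ANCOVA paragraph.

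The cost is a wording change and one contrast statement in the program, with no new data and no patient burden. The change does not remove the limitation that TEADA status is a post-randomization classification; the report should say so.

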#### 6.12.8. Patient Narratives

Patient narratives will be provided for all patients in the study who experience any of the following "notable" events prior to data cutoff for the submission:

- deaths
- serious adverse events
- discontinuations from study (or study drug) due to AEs
- pregnancy

A list of patients who meet the criteria for narratives will be provided.

#### 6.13. Subgroup Analyses

#### 6.13.1. Subgroup Analyses for HbA1c

The following subgroups will be analyzed for HbA1c if there are sufficient numbers of patients per group (for example, at least 10% in each group) using data collected from all randomized patients prior to discontinuation of IP through Week 26:

- age (<40,  $\geq40$  years)
- hemoglobin A1c stratum ( $\leq 8.5\%$  vs. > 8.5%)
- sex (male vs. female)
- body mass index (<25 vs.  $\geq$ 25, and <30 vs.  $\geq$ 30 kg/m^2)
- duration of diabetes (using the median as the cut-off)
- race
- country
- baseline 1-hour PPG excursion (≤ baseline median, > baseline median)
- baseline 1-hour PPG (PPG  $\leq 180 \text{ mg/dl}, >180 \text{ mg/dl})$

- baseline 2-hour PPG excursion (≤ baseline median, > baseline median)
- baseline 2-hour PPG (PPG  $\leq 180 \text{ mg/dl}, >180 \text{ mg/dl})$
- type of basal insulin during the lead-in period (glargine U-100 vs. degludec U-100)
- prandial insulin dosing plan (carbohydrate counting or pattern adjustment)

Analyses for HbA1c and change from baseline in HbA1c will be performed using an MMRM model that includes the same fixed effects given for the primary analysis model plus factors of subgroup, 2-way interaction of subgroup and treatment, 2-way interaction of subgroup and visit, and 3-way interaction of treatment, visit and subgroup. The interaction of subgroup and treatment at the primary endpoint will be evaluated to assess the treatment by subgroup interaction. When analyzing HbA1c stratum as a subgroup the baseline HbA1c will not be included as a covariate to avoid confounding. The subgroup interaction effect will be evaluated using a significance level of 0.10, unadjusted.

Additional subgroup analyses may also be performed.

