#### 5.3. Method of Assignment to Treatment

Patients who meet all criteria for enrollment will be randomized to double-blind treatment at Visit 8. Assignment to treatment groups will be determined by a computer-generated random sequence using an interactive web-response system (IWRS). Patients will be randomized to 1 of the 2 treatment groups in a 1:1 ratio. Stratification will be by country (China vs. Other), HbA1c stratum ( $\leq 8.5\%$  vs. >8.5% at Visit 7), type of basal insulin during the lead-in period (glargine U-100 vs. degludec U-100), and use of metformin at study entry (yes vs. no).

Abbreviation: T = telephone visit.

a At Visit 2, patients on insulin glulisine, insulin aspart, regular human insulin, or premixed insulin will be transferred to insulin lispro. The patients' basal insulin regimen will be switched to insulin glargine U-100 once daily or to insulin degludec U-100 once daily. At Visit 8, patients will be randomized to either premeal insulin lispro or premeal LY900014 and continue their basal insulin regimen.

- b Titrate basal insulin
- c Titrate prandial insulin (insulin lispro or LY900014)
- d Patients will discontinue study insulins at Week 26.

Figure 5.1. Illustration of study design.

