#### 6.2. Adjustments for Covariates

Stratification will be by country (China vs. Other), HbA1c stratum ( $\leq 8.5\%$  vs. >8.5% at baseline), type of basal insulin during the lead-in period (glargine U-100 vs. degludec U-100), and use of metformin at study entry (yes vs. no). Stratification factors will be entered into the IWRS for randomization and also collected in the database by electronic case report form (eCRF) or central laboratory. The analysis models for efficacy endpoints will use the stratification factors as collected in the database.

For continuous analyses of HbA1c, the stratification factor of HbA1c stratum (baseline) will not be included. Instead, the continuous value of baseline HbA1c will be included in the analysis models.

Other analyses will include the stratification factors as noted in Sections 6.11 and 6.12.

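### The HbA1c-stratum subgroup model drops continuous baseline HbA1c for a reason that does not apply to the interaction it tests, at a modest cost in precision

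*SAP*

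**What the plan says.** SAP 6.13.1 fits each HbA1c subgroup with the primary model's fixed effects plus subgroup, subgroup-by-treatment, subgroup-by-visit and three-way terms. Two outcomes are planned: "Analyses for HbA1c and change from baseline in HbA1c will be performed using an MMRM model". The quantity of interest is named: "The interaction of subgroup and treatment at the primary endpoint will be evaluated to assess the treatment by subgroup interaction". The test level is also given: "The subgroup interaction effect will be evaluated using a significance level of 0.10, unadjusted".

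For the HbA1c stratum alone there is an exception: "When analyzing HbA1c stratum as a subgroup the baseline HbA1c will not be included as a covariate to avoid confounding". No other reason is offered.

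Elsewhere the continuous value is the rule. SAP 6.2 leaves the stratum out of continuous HbA1c analyses and says "Instead, the continuous value of baseline HbA1c will be included in the analysis models". The primary model in SAP 6.11.1 follows this. On allocation, SAP 5.3 says "Patients will be randomized to 1 of the 2 treatment groups in a 1:1 ratio" and "Stratification will be by country (China vs. Other), HbA1c stratum", with the cut at 8.5% using the Visit 7 value. SAP Table 6.2 takes baseline HbA1c as the last of Visits 7-8.

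**The concern.** A covariate confounds a treatment comparison only if it is systematically related to treatment. Baseline HbA1c precedes randomization, and treatment is allocated at random with HbA1c stratum as a stratification factor. Baseline therefore cannot systematically differ between arms within a stratum, and it cannot distort the contrast of the two within-stratum effects. It is related to the stratum, because the stratum is baseline HbA1c cut in two. That makes the stratum main effect hard to separate from the baseline slope, but SAP 6.13.1 does not test the main effect.

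Three things are given up:

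- The variation in outcome that baseline explains within a stratum goes into the residual.
- A chance baseline imbalance between arms within a stratum is not adjusted for.
- The analyses of actual HbA1c and of change no longer give the same answer. With baseline in the model they are the same model for the interaction; without it they are not.

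**Working it through.** **The plan's own figure.** SAP 5.2 gives a margin of 0.4%, SD 1.1%, 149 completers per arm and 87% power.

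- SE = 1.1 × √(2/149) = 0.1274.
- Power = Φ(0.4/0.1274 − 1.96) = Φ(1.18) = 88.1%, or 87.9% with the t distribution.
- 298/0.85 = 350.6, against about 350 planned.

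The figures reproduce. The SD of 1.1% is the only variability figure in the documents, and I use it as the SD of change.

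**Formula.** Without baseline, the residual variance in stratum s rises from σ² to σ² + c²Vₛ. Here Vₛ is the variance of baseline within the stratum, and c is the slope of the outcome on baseline. If the slope of change is b, then c = b for change and c = 1 + b for actual HbA1c. The variance inflation is 1 + c²V/σ², with σ² = 1.1² − b² × (baseline variance). V is either the average of Vₛ over patients or, for the interaction, the average weighted by 1/nₛ.

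**Assumed inputs (not in the documents).** Baseline normal with mean 8.0-8.3% and SD 0.7-0.8; b from −0.3 to −0.5.

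**Worked case: mean 8.15, SD 0.8, b = −0.4.**

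- Cut: z = (8.5 − 8.15)/0.8 = 0.4375, so 33.1% of patients lie above 8.5%.
- Truncated-normal variances: 0.300 at or below 8.5% and 0.178 above it.
- Patient average: 0.669 × 0.300 + 0.331 × 0.178 = 0.260. Interaction-weighted: 0.331 × 0.300 + 0.669 × 0.178 = 0.218.
- σ² = 1.21 − 0.16 × 0.64 = 1.108.
- Change: 0.16 × 0.260/1.108 = 3.8% (interaction-weighted 3.1%).
- Actual: 0.36 × 0.260/1.108 = 8.4% (interaction-weighted 7.1%).

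**Over the assumed ranges.**

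| Outcome | Variance inflation, patient average | Interaction-weighted |
|---|---|---|
| Change | 1.4% to 6.8% | 1.2% to 5.4% |
| Actual HbA1c | 4.3% to 12.2% | 3.5% to 9.7% |

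In rounded terms this is about 1-7% for change and 4-12% for actual. If b = 0 the loss for change is zero.

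**Simulation.** Least squares at Week 26 only, n = 298, 1:1 within stratum, 8,000 replicates per scenario, test at 0.10, true interaction −0.5 for power. With baseline kept, the change and actual results are identical, so they share one entry.

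| Baseline SD, slope, residual SD | Interaction SE: kept / dropped (change) / dropped (actual) | Power: kept / dropped (change) / dropped (actual) |
|---|---|---|
| 0.8, −0.2, 1.08 | 0.272 / 0.273 / 0.291 | 57.5% / 57.3% / 53.6% |
| 0.8, −0.4, 1.05 | 0.264 / 0.269 / 0.275 | 59.3% / 58.4% / 56.4% |
| 0.8, −0.4, 0.70 | 0.176 / 0.183 / 0.192 | 88.1% / 86.1% / 82.9% |
| 1.0, −0.6, 0.92 | 0.225 / 0.243 / 0.233 | 71.7% / 65.6% / 68.9% |

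In every scenario the mean interaction estimate was within about 0.005 of the truth, with or without baseline. Rejection under no interaction was about 9-10% either way. The only SE that fell on dropping baseline was that of the stratum main effect (for change in the first scenario, 0.250 to 0.192). The third and fourth scenarios lie outside the assumptions used for the headline range and show how the loss grows with a smaller residual or a steeper slope.

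**The case against.** **Collinearity and LS means.** The SAP's wording may be loose language for collinearity, and the collinearity is real. SAP 6.1 also displays LS means from the models. If baseline is kept and the LS means are evaluated at one overall mean of, say, 8.0-8.3%, that value cannot occur in the upper stratum. Omitting baseline gives means that describe each stratum as observed. This point stands, and the fix must deal with it. It does not rescue the stated reason, because neither the treatment differences nor the interaction depends on the baseline value chosen: the model has no treatment-by-baseline term.

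**The SAP's own convention.** SAP 6.2 uses the stratum or the continuous value, one in place of the other, and 6.13.1 can be read as the same swap in reverse. That is fair, so I do not call this a contradiction. The difference is that here the stratum is the subgroup under study, and nothing prevents both terms from being in the model.

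**Randomization and analysis strata.** Randomization used the Visit 7 value. The analysis uses database values, with baseline the last of Visits 7-8, so the two strata need not coincide for every patient. Both values precede randomization, so the conclusion holds.

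**Stronger readings.** A reader might infer that the subgroup result is biased or its error rate inflated; the simulation shows neither. A reader might also infer a large loss of power in the model's most important covariate. The documents do not say how strongly baseline predicts the outcome and give no power for any subgroup test, so that cannot be claimed.

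**Conclusion.** The point holds as a minor one. Omitting baseline HbA1c removes no confounding from the quantity SAP 6.13.1 tests, and it introduces no bias. It costs precision whenever baseline predicts the outcome within a stratum: about 1-7% in variance for change and 4-12% for actual HbA1c. Those sizes rest on the assumed baseline mean, SD and slope and on reading the SAP's 1.1% as the SD of change. The calculation is for a single visit, not the full MMRM. The direction does not depend on these assumptions, except that the loss vanishes for change at a zero slope.

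The analysis is one of many subgroup factors, tested at 0.10 without adjustment and outside the multiplicity scheme. The primary noninferiority test and the HbA1c superiority test keep continuous baseline, and the postprandial excursion tests use a separate model, so no confirmatory conclusion is affected.

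**What to change.** Delete the sentence in SAP 6.13.1, so that the HbA1c-stratum model carries continuous baseline HbA1c like the other HbA1c subgroup models. Add a line that displayed LS means for each stratum are evaluated at that stratum's own mean baseline.

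This needs no new data and no protocol change. The cost is that the stratum main effect becomes less interpretable, which is small because it is not tested. If the sponsor wants the model without baseline, it can be kept as a sensitivity analysis with the reason restated as collinearity.
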